5.2.2. Analyses for Continuous Data

5.2.2.1. Annual Decline Rate of Antibody Response

To calculate the annual decline rate of antibody response on NT, the NT titers measured at each blood sampling time point (including Study 700401 post-booster Visit, and Study B9371021 visits 1, 2, 3, 6, 7, 8, 9, 10) will be logarithmically transformed. These log transformed data will be used as dependent variable, with days after first booster dose (from study 700401) as independent variable, to calculate the annual decline rate, using regression model for each subject. The slope from the model multiplied by 365 is considered as the estimated annual decline rate for each subject. Summary statistics on the estimated annual decline across all subjects will then be presented.

Subjects with missing assay data at 38-month and 46-month after the first booster dose will not be included in this analysis. In addition, subjects with a more than 4-fold increase in TBE antibodies between successive visits will be excluded from the analysis.

Calculation of the decline rate:

- Perform linear regression of the log transformed results for each subjects;
- Annual decline rate=slope of regression line * 365;
- Calculate descriptive statistics for the annual decline rate across all subjects.

A similar analysis will be performed for the ELISA data.

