### 10.3.2 Study visits

#### 10.3.2.1 Blood draw (investigation of TBE antibody persistence)

**Visit 1:** 38 months  $\pm$  60 days after the booster vaccination in Study 700401ii.

All subjects who were administered the first booster vaccination in Study 700401 will be invited for this visit. Subjects with relatively low TBE serum antibody levels (as described further) will proceed to Visit 4 (Booster vaccination) and Visit 5 (Post-booster Visit), as applicable (see [Figure 20.1-1](#), [Supplement 20.1](#)).

**Visit 2:** 46 months  $\pm$  30 days after the booster vaccination in Study 700401.

This visit will only be applicable for those subjects who have not yet received the second booster vaccination. Subjects with relatively low TBE serum antibody levels will proceed to Visit 4 and Visit 5 (see [Figure 20.1-1](#), [Supplement 20.1](#)).

**Visit 3:** 58 months  $\pm$  30 days after the booster vaccination in Study 700401.

This visit will only be applicable for those subjects who have not yet received the second booster vaccination. Subjects with relatively low TBE serum antibody levels will proceed to Visit 4 and Visit 5 (see [Figure 20.1-1](#), [Supplement 20.1](#)).

**Visit 6:** 70 months  $\pm$  30 days after the booster vaccination in Study 700401.

**Visit 7:** 82 months  $\pm$  30 days after the booster vaccination in Study 700401.

**Visit 8:** 94 months  $\pm$  30 days after the booster vaccination in Study 700401.

**Visit 9:** 106 months  $\pm$  30 days after the booster vaccination in Study 700401.

**Visit 10:** 118 months  $\pm$  30 days after the booster vaccination in Study 700401.

These additional blood draw visits are only applicable for subjects who have not yet received the second booster vaccination. Subjects with relatively low TBE serum antibody levels will proceed to Visit 4 and Visit 5 (see [Figure 20.1-2](#), [Supplement 20.1](#)).

---

ii The 29 subjects who were administered the first booster vaccination at the 4 year time point in Study 700401 and who will enter the current study in 2010 will have their Visit 1 at 34 months  $\pm$  60 days. For Visit 2 and Visit 3 the schedule is to be followed as described in the protocol.

The following assessments will be performed:

- Verification of the signed and dated informed consent/assent of the subject prior to any procedures being done (at Visit 1 ONLY);
- Inclusion and exclusion criteria (see Section 9.1 and Section 9.2);

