### 10.3.2.2 Booster Vaccination Visit

**Visit 4:** (40 months  $\pm$  60 days, or 48, 60, 72, 84, 96, 108, or 120 months  $\pm$  30 days after the booster vaccination in Study 700401, as applicable (see [Figure 20.1-1](#) and [Figure 20.1-2](#), [Supplement 20.1](#)iii).

A booster vaccination will be administered to subjects who may not be protected against TBE for an entire further tick season, as determined by antibody levels detected at each blood draw (NT titer  $\leq$  20 and / or ELISA value  $\leq$  126 VIEU/ml).

For subjects who do not receive their second TBE booster vaccination during the entire course of this study due to sufficiently high TBE virus antibody levels, a booster vaccination will be offered free of charge at an appropriate time point outside the scope of this clinical study.

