2.2.2. Study Subjects Selection and Process

A total of 179 children, adolescents and young adults who received their first TBE booster vaccination in the precedent Study 700401 were enrolled to assess seropersistence of TBE antibodies at yearly intervals from approximately 3 years (38 months) to 10 years (118 months) after the first booster vaccination (as applicable), as well as antibody response to a second booster vaccination with either FSME-IMMUN 0.25 ml Junior or FSME-IMMUN 0.5 ml according to the subject's age.

Subjects who may not be protected against TBE for an entire further tick season (NT titer ≤ 20 and / or ELISA value ≤ 126 VIE U/ml) will be invited to receive the second booster vaccination at either the 40, 48, 60, 72, 84, 96, 108, or 120 month time point.

Figure 1. Study Design

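### The annual decline rate averages per-subject slopes although follow-up ends on a low titre, so it is not protected from bias

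*SAP*

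**What the plan says.** SAP 5.2.2.1 fits one least-squares line per subject to log titre against days since the first booster ("Perform linear regression of the log transformed results for each subjects"), multiplies the slope by 365, and closes with "Calculate descriptive statistics for the annual decline rate across all subjects". It specifies no weighting and no joint model. The time points are listed as "including Study 700401 post-booster Visit, and Study B9371021 visits 1, 2, 3, 6, 7, 8, 9, 10".

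Two exclusions apply. The first is "Subjects with missing assay data at 38-month and 46-month after the first booster dose will not be included in this analysis". The second is that "subjects with a more than 4-fold increase in TBE antibodies between successive visits will be excluded from the analysis".

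Who has a long series is decided by the titres themselves. Under SAP 2.2.2, subjects with "NT titer ≤ 20 and / or ELISA value ≤ 126 VIE U/ml) will be invited to receive the second booster vaccination". Protocol 10.3.2.2 gives the booster to subjects judged possibly unprotected, "as determined by antibody levels detected at each blood draw". Of Visits 2 and 3, Protocol 10.3.2.1 says "This visit will only be applicable for those subjects who have not yet received the second booster vaccination", and it limits Visits 6 to 10 in the same way.

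Protocol 13.4.2 asks for the pre-booster immunogenicity analysis by the three Study 209 age classes. SAP 5.2.2.1 mentions only a summary across all subjects.

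**The concern.** The last reading of a boosted subject is, on average, lower than that subject's true level at the time, because a low reading is what ended the series. A line through a short series ending on such a reading is on average too steep. The fewer the points, the stronger the effect.

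The Month 38/46 exclusion acts on the same subjects and can be read in two ways. A subject boosted after Visit 1 has two values: the Study 700401 post-booster value and Month 38. If exclusion needs both months to be missing, this two-point slope stays in. If either missing month is enough, the subject goes out, and with that group go the fastest decliners.

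The study is meant to inform the booster interval (Protocol 6.6.2), and rates of this type justified the NT cut-off of 20 in Protocol 7.1. A summary whose error depends on assay noise, on the share boosted early and on an ambiguous sentence is a weak basis for that use.

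**Working it through.** **Step 1: the plan's own figures.** Protocol 7.1 gives annual declines of -0.50, -0.38 and -0.46 on a log scale and says that a titre of 20 falls to 12.2, 13.6 and 12.6. With natural logs:

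- 20·exp(-0.50) = 12.13
- 20·exp(-0.38) = 13.68
- 20·exp(-0.46) = 12.63

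These agree within the rounding of the rates. The scale is therefore the natural log, used below.

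**Step 2: inputs.**

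- From the documents: draws at about Month 1 and at Months 38, 46, 58, 70, 82, 94, 106 and 118; exit at the first NT ≤ 20 from Month 38; about 175 participants.
- Assumed, because the documents do not give them: post-booster GMT 300, between-subject SD of log titre 0.8, true mean slope -0.450, slope SD 0.15, residual SD 0.4, linear decline on the log scale. The ranges tried are in Step 4.

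**Step 3: base case by number of points in the series (large simulated sample).**

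| Points | Share | True mean slope | Mean fitted slope |
|---|---|---|---|
| 2 (stopped at Month 38) | 0.095 | -0.573 | -0.663 |
| 3 | 0.091 | -0.553 | -0.598 |
| 4 | 0.143 | -0.535 | -0.565 |
| 5 | 0.158 | -0.499 | -0.517 |
| 6 | 0.137 | -0.460 | -0.469 |
| 7 | 0.105 | -0.420 | -0.424 |
| 8 | 0.076 | -0.383 | -0.386 |
| 9 | 0.195 | -0.276 | -0.271 |

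Mean = Σ(share × slope).

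- True slopes, all rows: -0.450.
- Both-missing reading, fitted slopes, all rows: -0.471, which is 0.021 too steep.
- Either-missing reading, first row dropped: (-0.4708 + 0.095 × 0.663)/0.905 = -0.451.
- True mean of those retained: (-0.4502 + 0.095 × 0.573)/0.905 = -0.437.

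The either-missing result is close to the truth only because two errors cancel. Losing the fast decliners moves the true mean from -0.450 to -0.437, and low-reading selection moves the estimate back by 0.014.

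**Step 4: trials of 175 subjects.** Standard error in brackets. The first three rows have GMT 300 and true slope -0.450; the last has GMT 600 and true slope -0.300. The mixed model has a random intercept and slope and uses the same truncated data.

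| Setting | Both-missing | Either-missing | Mixed model |
|---|---|---|---|
| Residual SD 0.2 | -0.4547 (0.0122), +1.0% | -0.4408 (0.0123), -2.0% | -0.4509 (0.0123) |
| Residual SD 0.4 | -0.4717 (0.0138), +4.8% | -0.4510 (0.0130), +0.2% | -0.4500 (0.0136) |
| Residual SD 0.6 | -0.4952 (0.0164), +10.0% | -0.4651 (0.0148), +3.4% | -0.4510 (0.0169) |
| Slope -0.300, residual SD 0.4 | -0.3070 (0.0127), +2.3% | -0.3049 (0.0125), +1.6% | -0.2991 (0.0125) |

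Plus means too steep, minus too flat. In these rows the both-missing error is 0.4 to 2.8 standard errors (0.0047/0.0122 to 0.0452/0.0164). The either-missing error is at most about 1.0 (0.0151/0.0148).

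A grid of 540 scenarios was also run: GMT 150–1000, slope -0.50 to -0.15, slope SD 0.05–0.20, residual SD 0.2–0.5, intercept–slope correlation -0.4 to 0.4.

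- Both missing: 0 to 16.8% too steep, median 2.2%, never too flat.
- Either missing: from 18.5% too flat to 11.6% too steep, median 0.7% too steep, within 0.5% in 23% of scenarios.
- With the protocol's own slopes and GMT 300 or 600: 0.5 to 8.3% too steep if both; 8.8% too flat to 6.6% too steep if either.

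**Step 5: is equal weighting the cause?** Weighting the base-case slopes by number of points gives about -0.42 (both) and -0.41 (either) against -0.450. That is worse than equal weights in the either-missing case and too flat in both, because long series belong to slow decliners.

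**Step 6: where the mixed model is less good.**

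- Two-phase decline: -0.213 to -0.215 against a truth of -0.210 to -0.209, about 1.5–2.7% off. The planned method is 5.1–8.0% off (both) or 4.2–6.0% (either).
- Assumed 6-fold rises in 1–2% of subjects per visit: -0.439 to -0.430 if those subjects stay in; -0.447 to -0.445 if the SAP's 4-fold exclusion is kept.

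**The case against.** The strongest reply has four parts.

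- **The wording may favour the milder reading.** SAP 5.2.1 and Protocol 13.3 use the same pairing of Months 38 and 46 to mean each visit, and the post-booster, Month 38 and Month 46 values make up the three points needed for extrapolation. This is fair inference. However, the three-point condition is written for estimating missing values, not for the decline summary, so it does not settle the matter.
- **Under that reading the error may vanish.** This stands. A reader might infer that the estimate is biased whichever way the rule is read; the base case, at 0.2%, shows that this is too strong. What can be said is that the method gives no protection, since the near-zero result is a cancellation.
- **The mechanism can be overstated.** A reader might infer that every boosted subject's slope is too steep, or that equal weighting is at fault. Neither holds. Only about 55–61% of boosted subjects had a fitted slope steeper than their true one, and weighting by number of points can do harm (Step 5).
- **Little hangs on it.** SAP 5.1 calls the study descriptive. Moving the slope from -0.450 to -0.4717 takes a titre of 20 to 12.5 instead of 12.8 after a year, a smaller change than the protocol's own spread of 12.2 to 13.6 between age classes. This stands, and it limits the weight of the point.

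A mixed model is not assumption-free either. Exit can follow ELISA as well as NT, and the simulations used the NT trigger only.

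**Conclusion.** The point holds as a modest one. Averaging separate slopes when follow-up ends on a measured low value leaves the mean annual decline open to bias. Under the both-missing reading it is on average too steep, by about 2–10% in the central settings, 1.0% when assay noise is low, and 0 to 16.8% over the grid. Under the either-missing reading the sign is not fixed and the error is typically within about 3%, with larger values in some scenarios. It is negligible if few subjects reach the trigger. All sizes rest on the assumed titres, variances and linear log decline. Declined boosters were not modelled, and the 4-fold exclusion was examined only in Step 6.

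A reader might go on to infer that the NT 20 cut-off is undermined, or that the primary seropositivity result is shown to be biased because SAP 5.2.1 extrapolates from the same regressions. The documents do not support the first: Protocol 7.1 set the cut-off from data after the primary series. The second is a separate question that this check did not measure. No test or sample size rests on the decline rate.

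**What to change.** In SAP 5.2.2.1:

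1. Make the main estimate a linear mixed model (REML) of natural-log titre on years since the first booster, with random intercept and slope per subject and fixed slopes by age class, as Protocol 13.4.2 requires. Use all titres before the second booster, with no Month 38/46 requirement. Report slopes with 95% CIs.
2. Keep the existing exclusion of subjects with more than 4-fold rises.
3. Check for curvature in time.
4. Add a joint NT/ELISA model as a sensitivity analysis, because either assay can trigger exit.
5. Keep the averaged per-subject slopes as supportive, for comparison with Protocol 7.1, and state whether the Month 38/46 exclusion there means either or both missing.

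The cost is SAP wording, one main model per assay and one joint model, all on data already collected. In the base case the standard error is about the same (0.0136 against 0.0138 and 0.0130). The downside is reliance on normal random effects and log-linear decline.

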5.2.2.2. GMT

To estimate the antibody response from approximately 3 years to 10 years after the first booster vaccination (from precedent study 700401), NT titers and ELISA concentrations measured at each blood sampling time point (including extrapolated from regression model for subjects with booster dose or early withdrawals from [Section 5.2.2.1](#), and the available assay results) after the first booster will be logarithmically transformed for analysis and GMTs/GMCs will be computed with 95% CI for each assay. The analysis will be applied to the [‘Per Protocol’ Analysis Set](#). For the [mITT Population](#), GMTs/GMCs with 95% CI will be computed using all available NT titers and ELISA concentrations, ie, no extrapolation from regression model will be done for subjects with booster dose or early withdrawals.

To estimate the antibody response after the second booster vaccination within this current study, NT titers and ELISA concentrations measured at the postbooster visit will be logarithmically transformed for analysis and GMTs/GMCs will be computed with 95% CI for each assay. The analysis will be applied to both the [‘Per Protocol’ Analysis Set](#) and [mITT Population](#). Data will be presented for each year, as well as for the combined postbooster.

The 2-sided, 95% confidence intervals for the GMTs/GMCs will be constructed by back transformation of the confidence intervals for the mean of the logarithmically transformed titers or concentrations computed using the Student t distribution.

5.2.2.3. GMFR

Fold-rise of NT titers from the prebooster visit to postbooster visit will be logarithmically transformed for analysis. The analysis will be applied to both the [‘Per Protocol’ Analysis Set](#) and [mITT Population](#). Data will be presented for each year, as well as for the combined.

Two (2)-sided, 95% confidence intervals will be constructed by back transformation of the confidence intervals for the mean of the logarithmically transformed fold-rise computed using the Student t distribution.

GMFR on ELISA concentration will be analyzed similarly to NT.

5.2.2.4. RCDC

The empirical reverse cumulative distribution curves (RCDCs) will be presented graphically for NT and ELISA at each visit, for the per-protocol analysis set. If subjects were boosted or an early withdrawal, the extrapolated antibody response (refer to [Section 5.2.2.1](#) and [Section 5.2.1](#)) will be combined with nonmissing assay data for the time point. The graph will be presented for the total per-protocol analysis set as well as for each age group based on age at the primary dose (refer to [Section 3.3](#)).

The analyses will only be applied to the [‘Per Protocol’ Analysis Set](#).

5.2.3. Analyses for Binary Data

All of the binary endpoints will be descriptively summarized along with the exact 2-sided 95% confidence interval (or Clopper-Pearson confidence limit) for the proportion. The exact confidence interval for proportion will be computed using the F distribution. If r equals the number of responses and n equals the number of subjects, then it follows that $p = r / n$ is the estimate of the proportion of responses. An exact 95% confidence interval can be computed by solving the following 2 equations. For the lower limit p_L , use:

$$p_L = \frac{rF_L}{(rF_L + (n - r + 1))} \text{ and for the upper limit } p_U, \text{ use } p_U = \frac{(r + 1)F_U}{(n - r) + (r + 1)F_U}$$

where F_L is the quantile from the F distribution for $\alpha=0.025$, with numerator degrees of freedom equal to $2r$ and denominator degrees of freedom equal to $2(n-r+1)$. F_U is the quantile from the F distribution for $\alpha=0.975$, with numerator degrees of freedom equal to $2(r+1)$ and denominator degrees of freedom equal to $2(n-r)$. When r equals 0, F_L should be set equal to 1.0 so p_L equals 0. When r equals n , F_U should be set equal to 1.0 so p_U equals 1. The confidence interval using the F distribution is described in Collett (1991¹) and implemented in SAS procedure (ie, PROC FREQ).

To estimate the seropositivity rate as determined by NT from approximate 3 years to 10 years after the first booster vaccination (from precedent study 700401), the proportion of subjects with $NT \geq 10$ at each blood sampling time point (including extrapolated from regression model for subjects with booster dose or early withdrawals from [Section 5.2.2.1](#), and the available assay results) after the first booster will be summarized with the exact 95% CI. Similarly, the proportion of subjects with $ELISA > 126$ at each blood sampling time point (including extrapolated results) after the first booster will be summarized with the exact 95% CI. The analysis will be applied to '[Per Protocol](#)' Analysis Set. For [mITT Population](#), which will include all available NT titers and ELISA concentrations, ie, no extrapolation from regression model will be done for subjects with booster dose or early withdrawals.

To estimate the seropositivity rate after the second booster vaccination within this current study, the proportion of subjects with $NT \geq 10$ and proportion of subjects with $ELISA > 126$ will be summarized at postboost vaccination visit. The analysis will be applied to both '[Per Protocol](#)' Analysis Set and [mITT Population](#). Data will be presented for each year, as well as for the combined postbooster.

A logistic regression model will also be applied to examine the seropositive rate at each visit with the covariates (age at first booster dose from study 700401, gender, and BMI). The analyses will only be applied to the '[Per Protocol](#)' Analysis Set. Extrapolated values will be included in the analysis.

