4. ANALYSIS SETS

4.1. Full Analysis Set

An All-Enrolled Population will be defined as the Full Analysis Set, which consists of all subjects enrolled into the study. Any subjects who consented are included in the population. Subject disposition, history of tick bites, and demography will be presented for this population.

4.2. 'Per Protocol' Analysis Set

This analysis set is the primary analysis population for immunogenicity.

This Per-Protocol population includes subjects who:

1. Have been enrolled (consented) and meet all inclusion/exclusion criteria at all visits.
2. Have available assay results (ELISA or NT) at any blood sampling visit.
3. Have no other major protocol violations.

Above listed items 1 & 2 will be determined by computerized checks of the data, while item 3 will be determined by clinical review as these are considered as major protocol violations per the original protocol, which will eventually be entered into the database from Protocol Deviation (PD) case report form entries.

Subjects with major protocol deviations will be excluded from the primary analysis population, or in some instances, the ELISA and NT results affected by a protocol deviation at certain visit(s) will be excluded from the analysis.

If a subject meets the exclusion criterion 2, which is that subject has a history of infection with or vaccination against other flaviviruses (eg, Dengue fever, yellow fever, Japanese B encephalitis) since his/her first booster vaccination in Study 700401, the subject's affected ELISA results will be excluded from the analysis due to cross-reactivity. There is no cross-reactivity with the NT, so the NT results will be included in the analysis. The subject will be included in Per-Protocol population, under condition that he/she satisfies the rest of the conditions in above items 1 to 3.

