5.2. General Methods

5.2.1. Methods to Manage Missing Data

In general, only subjects with available data will be included in the statistical analysis.

Missing values for antibody titer at 38 and 46 months will neither be replaced nor estimated. Any missing values at later time points (ie, 58, 70, 82, 94, 106 and 118 months) due to early withdrawal or second booster vaccination within this current study, will be estimated if at least three data points are available, assuming an exponential decline in antibody titers in time (calculated as described in [Section 5.2.2.1](#)).

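### From about Month 58 the primary seropositivity rate counts per-subject extrapolations as measured titres and drops the earliest-boosted subjects, so it can be biased in either direction and its exact 95% CI does not show this

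*SAP*

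**What the plan says.** SAP 4.2 says of the Per Protocol set: "This analysis set is the primary analysis population for immunogenicity". For that set, SAP 5.2.3 computes the NT rate at each visit from assay results together with predicted values, "including extrapolated from regression model for subjects with booster dose or early withdrawals from" SAP 5.2.2.1. It does the same for ELISA: the proportion "at each blood sampling time point (including extrapolated results) after the first booster will be summarized with the exact 95% CI". The interval is the "exact 2-sided 95% confidence interval (or Clopper-Pearson confidence limit) for the proportion".

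SAP 5.2.1 does not estimate titres missing at Months 38 and 46. Later ones, missing because of withdrawal or the second booster, "will be estimated if at least three data points are available, assuming an exponential decline in antibody titers in time". The line is fitted to each subject's own log titres (SAP 5.2.2.1). It uses the Study 700401 post-booster visit plus Visits 1-3 and 6-10, and leaves out subjects with missing Month 38 and 46 data.

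The extrapolated values also enter the GMTs/GMCs (SAP 5.2.2.2), the logistic regression (SAP 5.2.3) and the RCDCs, where they "will be combined with nonmissing assay data for the time point". No section attaches an error to them.

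Most of the gaps arise by design. Subjects with NT at or below 20 and/or ELISA at or below 126 are invited for the booster. Protocol 10.3.2.1 says of Visits 6-10: "These additional blood draw visits are only applicable for subjects who have not yet received the second booster vaccination". For the mITT set, "no extrapolation from regression model will be done for subjects with booster dose or early withdrawals".

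**The concern.** Two features of the rule distort the rate, in opposite directions.

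- **Extrapolated subjects.** A boosted subject's line usually ends on the reading that triggered the booster. That reading is selected for being low, so it tends to carry negative assay error, and the line projects this forward for up to 72 months. If antibody decline slows with time, a straight line on the log scale also falls too far.
- **Dropped subjects.** A subject boosted after Visit 1 has two points, about Month 1 and Month 38, and no Month 46 value. The three-point condition is not met, so the subject is never extrapolated and leaves the denominator. These are the lowest responders.

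This concerns the primary endpoint at the visits for which follow-up was taken to 10 years. Under a range of assumed inputs, 37-83% of the Month 118 values would be predicted. Protocol 6.6.2 and 7.1 intend the results to inform booster intervals.

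**Working it through.** **1. The plan's own figures.** Protocol 13.1 states a distance of at most 5.8 points at n = 175 and a rate near 90%. Clopper-Pearson gives a lower distance of 5.48 points at 157/175 (89.7%) and 5.76 at 154/175 (88.0%). The figure holds for measured statuses and covers sampling error only.

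The decline rates in Protocol 7.1 are on the natural-log scale: 20·exp(-0.50) = 12.1, 20·exp(-0.38) = 13.7 and 20·exp(-0.46) = 12.6, against the stated 12.2, 13.6 and 12.6.

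**2. First affected visit.** Month 58 is affected if the Study 700401 post-booster titre counts as one of the three points (Months 1, 38, 46). If it does not, the first affected visit is Month 70. SAP 5.2.1 does not say which.

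**3. Leverage of the last reading.** For draws at Months 1, 38 and 46, the mean is 28.33 and Sxx = 27.33² + 9.67² + 17.67² = 1152.7.

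- SE of the line at Month 118: sqrt(1/3 + 89.67²/1152.7) = 2.70 residual SDs. At Month 82: sqrt(1/3 + 53.67²/1152.7) = 1.68.
- Adding residual error for a single titre at Month 118: sqrt(2.70² + 1) = 2.88.
- Weight of the Month 46 reading in the Month 118 prediction: 1/3 + 89.67 × 17.67/1152.7 = 1.71.

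An error in the last reading is therefore amplified.

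**4. Simulation of the SAP rule.** There were 1500 trials of 175 subjects, with the three-point, Month 38/46 and 4-fold rules applied. The target is the proportion of the whole cohort that would test NT ≥ 10 had nobody been boosted.

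These inputs are assumed because the documents do not give them: Month 1 GMT 300 or 600, between-subject ln SD 0.8, slope SD 0.12, residual ln SD 0.2-0.6, 3% dropout per visit. Decline is either log-linear or slows after Month 38 to 0.5 or 0.3 of the early slope. The mean annual slope of -0.45 is close to the average of the Protocol 7.1 rates, (0.50 + 0.38 + 0.46)/3 = 0.447. The trigger is NT ≤ 20. The ELISA trigger and titres below the assay limit are not modelled.

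With true rate T, dropped share d and true rate L among the dropped, the true rate among retained subjects is R = (T - d·L)/(1 - d). Dropping shifts the rate by R - T, and extrapolation shifts it by SAP - R. All entries are percentages or percentage points.

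| Scenario | Month | T | d, L | R | SAP | Dropping | Extrapolation | Net | Coverage of T |
|---|---|---|---|---|---|---|---|---|---|
| GMT 300, SD 0.2, log-linear | 58 | 89.6 | 9.9, 36.2 | 95.5 | 95.1 | +5.9 | -0.4 | +5.4 | 34.6 |
| GMT 300, SD 0.4, log-linear | 58 | 88.4 | 11.4, 46.6 | 93.8 | 92.7 | +5.4 | -1.1 | +4.3 | 63.8 |
| GMT 600, SD 0.4, log-linear | 118 | 42.2 | 4.9, 26.9 | 43.0 | 41.1 | +0.8 | -1.9 | -1.2 | 94.9 |
| GMT 600, SD 0.4, slows to 0.5 | 118 | 84.6 | 5.0, 56.9 | 86.1 | 76.0 | +1.5 | -10.1 | -8.6 | 21.8 |
| GMT 600, SD 0.4, slows to 0.3 | 118 | 95.3 | 5.0, 72.1 | 96.5 | 87.3 | +1.2 | -9.2 | -8.0 | 5.3 |

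The two parts sum to the simulated net within 0.1 (rounding).

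Among extrapolated subjects alone, the rate was too low in all seven runs, by 0.5 to 32 points.

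**5. Is the interval itself wrong?** At Months 58-118 in every run, the empirical SE was 0.97-1.04 times the binomial SE. The interval covered the rate that the rule itself estimates in 95-99% of trials. Each prediction uses only that subject's data, so the 0/1 statuses are independent. Prediction error enters as misclassification.

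**6. mITT.** Observed-only rates stayed at 89-100% when the true Month 118 rate was 24-95%, because subjects leave observation when their titres are low.

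**The case against.** The strongest defence is that the study is descriptive with no decision rule (SAP 5.1), the extrapolation is prespecified in both documents, and the endpoint is also reported without it in mITT. The two errors also partly cancel. In a separate log-linear simulation (179 subjects, Month 1 GMT 300, slope -0.3, residual SD 0.5), the Month 118 rate was 0.620 against 0.627 for the whole cohort, with coverage 0.94. The sizes depend on inputs that are not in the documents.

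Much of this stands. A reader might infer that the rate is simply biased low from Month 58. That is true of the extrapolated subjects but not of the cohort, because the dropped low responders push the rate up and the documents do not fix the net sign. A reader might also infer that the exact interval is too narrow because it lacks a prediction-error term. Step 5 shows that the binomial variance is right for what the rule estimates, so widening the interval alone would repair nothing.

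The defence does not settle the matter. Cancellation of two unrelated errors is not a safeguard, and it fails at Month 58 with fast decline and at Month 118 with slowing decline. The mITT analysis is biased high and cannot serve as a check. SAP 6.4.1 tabulates blood draws by visit but does not ask for the number of predicted values in each rate. The table shells are separate, so whether they show it cannot be judged.

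**Conclusion.** The point holds as a bias problem of unknown net sign. From about Month 58 (or Month 70, depending on how the three points are counted), the primary rate, GMTs/GMCs, RCDCs and logistic regression treat single extrapolations as measured titres, while the lowest responders are lost.

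Under the assumed inputs, whole-cohort bias in the rate ranged from +5.4 to -8.6 points. It was near zero in some log-linear scenarios, upward at Month 58 with fast decline from the lower titre level, and about -8 to -9 points at Month 118 if decline slows. Coverage ranged from nominal to 5%. The largest biases are similar to or larger than the 5.8 points in Protocol 13.1. Residual SD, titre level and decline shape drive the size, and the documents give no post-first-booster values for them. The rule should be changed before the final analysis.

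**What to change.** In SAP 5.2.1, 5.2.2.1 and 5.2.3, replace the per-subject lines as the source of missing values.

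- Fit one linear mixed model to all measured log titres after the first booster, with random intercept and slope. Include ELISA as an auxiliary outcome, since either assay can trigger the booster.
- Multiply impute Months 58-118 with parameter, subject and residual error. Combine rates, GMTs/GMCs and intervals by Rubin's rules, and base the RCDCs and logistic regression on the imputed sets.
- Include subjects boosted after Visit 1. State this as a change to the three-point condition in Protocol 13.3 and SAP 5.2.1.
- Add a sensitivity analysis with a non-linear, slowing decline. Imputation under a straight line would inherit that bias.
- Report measured and imputed counts at each visit.

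In the seven runs, a random intercept and slope model had bias of at most 0.1 point at Months 46-118. This is a best case, with the correct time shape and known variances.

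The cost is SAP text, a documented departure from Protocol 13.3 and some programming, with no new data. A pooled interval replaces the exact one and is slightly wider: about 17 points full width against about 15 at Month 118 in simulation.
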